The Indego exoskeleton was approved for use by the FDA in February of 2016 with individuals with spinal cord injury (SCI) at levels T4 and below for rehabilitation use, and for T7 and below for personal use in the home and community. Shepherd Center was instrumental in leading the multi-site clinical trials that led to the Indego FDA approval for persons with SCI.

Shepherd Center, in collaboration with Vanderbilt University and Parker Hannifin Corporation, has also led the clinical research efforts for use of Indego for persons with hemiparesis resulting from cerebrovascular accident (CVA) since 2012.

A publication from our earliest work using Indego with persons with CVA (Shepherd RRC project #510) can be found here: S. A. Murray, K. H. Ha, C. Hartigan, and M. Goldfarb, "An assistive control approach for a lower-limb exoskeleton to facilitate recovery of walking following stroke," Neural Systems and Rehabilitation Engineering, IEEE Transactions on, vol. 23, pp. 441-449, 2015. Shepherd Center Principal Investigator was [name] [name]

A second manuscript from an Indego trial for persons with CVA conducted in 2015 and 2016 as a collaborative effort between Shepherd Center, Vanderbilt University and Parker Hannifin Corporation (Shepherd RRC Project #660) has been submitted but not yet accepted for publication. A full copy of the manuscript is attached in this IRB submission: Spencer A. Murray, Student Member, IEEE, Clare Hartigan, Casey Kandilakis, Elizabeth Sasso, and Michael Goldfarb, Member, IEEE "A Preliminary Crossover Study of Exoskeleton Control Methodologies for Gait Rehabilitation Post-Stroke". Shepherd Center Principal Investigator was [name] [name]

The Indego User Manual is attached in this submission. In addition, videos and other Indego information can be found at www.Indego.com

STUDY SYNOPSIS**Primary Objective:**

- To demonstrate that the Indego® device is safe to use as a gait training intervention for persons with hemiplegia due to CVA.

Results of this multi-site study to include 40 subjects will be submitted to the FDA as part of a 510K Parker Hannifin submission to seek FDA approval for Indego use with persons following stroke.

Hypothesis:

- Indego can be safely used as a gait training intervention for persons with hemiplegia due to CVA for persons with mild, moderate or severe stroke.
- Indego can be safely used as a gait training intervention for persons with hemiplegia due to CVA for persons with acute (less than 2months), sub- acute (2-6 months) and chronic (greater than 6 months) onset.
- Following six Indego sessions, persons with hemiplegia due to CVA may show improvements in mobility when comparing pre- training measurements to post-training measurements.

Study Design:

Forty subjects in total will be enrolled across nine clinical sites: Shepherd Center (GA), Cedar Sinai Medical Center (CA), Rusk Rehabilitation (NY), Sheltering Arms (VA), St Charles Hospital (NY), Craig Hospital (CO), Kessler Foundation (NJ), Rehabilitation Institute of Chicago (Shirley Ryan AbilityLab, IL) and TIRR Memorial Hermann (TX). Subjects will be seen three times per week for two weeks.

Up to five subjects are expected to be enrolled at Shepherd Center.

	Session Content	Session Duration
Session 1	Consent Initial Evaluation and Fit	2 hours
Session 2	Indego Training Sessions	1 hour
Session 3		
Session 4		
Session 5		
Session 6	Indego Training Session Final Evaluation	2 hours

Study duration for each individual enrolled is two weeks. If a session is missed, attempts must be made to reschedule within the same week. The maximum amount of time the protocol may be interrupted or extended (due to illness, weather, other) is two weeks. The number of study visits remains the same.

Shepherd Center will be provided with an Indego® kit for the duration of the trial. This kit will include small (short), medium and large (tall) hardware components, all necessary padding options, and 2 hand held iPod touch operator controllers. Parker will provide “on call” engineering support.

Enrollment for PHIND_CVA01 will be on a rolling basis so that each site can enroll any number of subjects until the total subject number across sites reaches forty. Should a subject not complete all study sessions, an additional subject will be added to replace the person who did not complete the study. Data for persons who did not complete all sessions for the study will be analyzed separately.

Subjects may be enrolled from inpatient, day program, outpatient, post rehabilitation programs, or from home. Researchers will not attempt to have an equal representation among “programs” of when the subject was enrolled. However, the sponsor will attempt to have a mix of acute, sub acute and chronic conditions.

 - Fugl – Meyer Assessment (*to be assessed during PT evaluation only, for stratifying severity of stroke*)
 - Spasticity: Modified Ashworth Scale (MAS)
 - Bilateral upper and lower extremities
 - Strength
 - Manual Muscle Test (MMT) of upper and lower extremities
 - Strength will be tested even if the subject presents with MAS 0-3. The potential influence or limitation of the MAS score will be reflected in session notes
- **Activity (to be assessed WITHOUT Indego; Indego will be used during gait training only, not during mobility measures)**
 - Functional Ambulation Category (FAC)
 - Fast Gait speed (as measured during the 10 Meter Walk Test with 14 Meter Track)

SESSION DATA

Within each of the six sessions, the following parameters will be also monitored and recorded:

- Medications
- Skin Integrity – Pre/Post each session
- Vital signs – Pre/Post each session
- Pain – FLACC scale (Face, Legs, Activity, Cry, Consolability scale with pictorial images)
- Functional Ambulation Category (FAC)
- Adverse Events
 - Subject
 - Device
 - Falls
- Comments on Spasticity (Formal MAS only during sessions one and six)

SESSION GUIDELINES

- Therapists will make all attempts not to affect the subject's functional performances on mobility measures, however patient safety is priority. Levels of assistance provided to the subject will be recorded.
- Indego sessions should be scheduled to avoid fatigue and to work in collaboration with other inpatient or outpatient therapies.
- One study session allowed per day
- Concurrent therapies are allowed, but therapists should take into account adequate rest for the subject in the event they have other appointments the same day.
- A fall is defined as “An unintentional change in position coming to rest on the ground, floor, or onto the next lower surface (e.g. onto a bed, chair or bedside mat). The fall may be witnessed, reported by another person, or identified when the user is found on the ground. Falls include any fall whether it occurred at home or out in the community. Falls are not a result of an overwhelming external force (e.g., the user is pushed by another person). An intercepted fall occurs when the user would have fallen if he or she had not caught him or herself, or had not been intercepted by another person—this is still considered a fall “ Definition provided by FDA to Parker Hannifin on July 20, 2016 based on Centers for Medicare and Medicaid Service guidelines.

EXPECTED TIMELINE TO COMPLETE 40 SUBJECTS ACROSS SIX SITES:

- 40 subjects for 2 week intervention = 80 weeks/6 sites = 13 weeks per site (3.25 months)
- Depending on site enrollment, total study duration should last roughly 8 months.

EFICACY ENDPOINTS**Primary Endpoint:**

- To show that the Indego® device is safe and potentially effective at providing gait training intervention for persons with hemiplegia due to CVA.

Supportive and Exploratory:

- Assess vital sign and skin
- Assess pain
- Assess impact of Indego training related to mobility measures.
- Assess changes in spasticity

SAFETY MEASURES

- Subjects must meet all inclusion criteria and possess none of the exclusion criteria
- Subjects must have medical clearance to participate prior to consenting process.
- Vital signs will be taken before and after each session

- Skin checks will take place before and after each session
- An Indego® certified PT will be present for all sessions.
- Sponsor will provide “on call” engineering support for the duration of the study.
- The six clinical sites chosen for the study are all experts in the field of neurological rehabilitation.
- All Subject Adverse Events and Serious Adverse Events will be documented, reported and followed to resolution.
- All device related adverse events to include device malfunctions pertaining to the device hardware, software or hand held controller interface will be documented, reported and followed to resolution.

STATISTICAL MEASURES

Forty subjects must complete all sessions for the study to be concluded. If any subject is unable to complete all sessions, their data will be analyzed separately and reported as a sub set to the main report.

A total sample size of 40 participants and over 200 Indego training sessions for this study will yield reasonable statistical power in determining the safety of the device and potential differences between pre- and post-test values, one-sample means tests, and Pearson correlation coefficients. When conducting matched pairs t-tests for pre- and post-test differences, 40 participants will yield a power of 0.87, with an alpha level of 0.05 and an effect size of 0.50, an effect size value that falls within the medium range according to Cohen (1998).

Cohen, Jacob. *Statistical Power Analysis for the Behavioral Sciences*. Hillsdale (NJ): Lawrence Erlbaum Associates, Inc.; 1998.

Descriptive analyses will also be reported for medical history, severity and onset of CVA, subject evaluation measures, gait characteristics and subject/device adverse events.

RATIONALE

The following is paraphrased from S.A. Murray’s dissertation “Development and assessment of a control approach for a lower-limb exoskeleton for use in gait rehabilitation post stroke.” Vanderbilt University, 2016:¹

CVA is one of the leading causes of chronic disability in the United States. There are an estimated 6.6 million people having survived a cerebrovascular accident (CVA) and an estimated 610,000 first-incident CVAs occurring each year in the United States[1]. Restoration of gait functionality is often a high priority during rehabilitation in patients with lower-limb hemiparesis [2, 3]. This has thereby caused many to develop robotically-assisted gait-training devices in recent years.

While results vary in the highly-heterogeneous population of stroke patients, a recent meta-analysis found that electromechanically-assisted rehabilitation devices may improve the likelihood that a patient will recover the ability to walk independently [4]. Many control approaches have been proposed and described for the control of these robotic devices [5-15]. These control strategies can be roughly categorized as either a “trajectory-based controlled” or “non-trajectory-based controlled” type. Trajectory-based controllers dictate the spatiotemporal nature of joint movement; non-trajectory based controllers do not. Examples of the latter include force tunnels around the desired trajectory [8, 12, 14], teach-and-replay impedance based control strategies to generate subject-specific trajectories [16], and model-based strategies to target specific portions of the gait cycle [9, 17].

The following is paraphrased from S.A. Murray et. al 2019, currently in preparation for publication¹

A trajectory control approach can offer functional advantages relative to a non-trajectory control approach, such as the ability to consistently reproduce healthy gait kinematics, provide full movement assistance, and provide

¹ Note: These points of clarification added on April 17, 2019.

early therapy to subjects who may otherwise be non-ambulatory. Despite these potential advantages, researchers hypothesize that a trajectory-based control approach may allow patients to assume a *passive* role within the device, since the device is, in essence, providing full coordination and effort associated with movement. It is well-known that increased patient participation results in improved outcomes [18, 19], and therefore recovery is more likely if the machine promotes active rather than passive patient participation.

Thus, despite the advantages of a trajectory-based controller, researchers hypothesize that a non-trajectory-based control approach would place increased responsibility for coordination and movement on the patient, and would therefore require greater engagement, and thus presumably result in improved functional outcomes.

Use of Indego for the proposed study is a non-trajectory based controller approach. Use of the Indego controller for persons with stroke has been safely utilized in the following studies, previously approved by Shepherd Center Research Review Committee:

- Project #510: i-Step Long-Leg Orthosis (3 subjects with CVA enrolled. Study has been closed)
- Project #660: Engineering Assessment of the Indego® Software Controllers – Parker #ENG1 (8 subjects with CVA currently enrolled. Study remains active)

In previous Shepherd RRC approved studies, gait parameters were controlled and manipulated by Vanderbilt or Parker Engineers through a tethered cord from the Indego device to a laptop computer. For the proposed study, the gait parameters will be manipulated by the physical therapist through an iPod controller connected wirelessly to Indego using Bluetooth.

To date there have been no serious adverse events of falls using the Indego with persons with. No sites other than Shepherd Center have completed research using the Therapy Mode controller that was designed for persons with stroke and other neurological disorders.

The proposed study will allow a greater number of subjects and participating sites to evaluate the safety of the Therapy Mode Indego controller and assist in data collection for potential approval through the Parker 510 K submission by the FDA to use the Indego as a gait training tool for persons with hemiplegia due to stroke.

(Figure 1) Indego® ; total weight 26 pounds, 5 modular components, powered assist at the hip and knee joints, carbon fiber ankle foot orthoses is passive.

[figure not shown]

(Figure 2) Subject training in the Indego with PT assist and tethered control cord. In the proposed study the tethered cord will not be present, rather an Ipad touch will be used to communicate the subject settings to the Indego device through wireless Bluetooth.

Clinicians will have the option to modify 5 different groups of subject settings through the wireless Bluetooth Ipad touch controller:

1. Joint Neutrals,
2. Gravity Compensation
3. Stance Support
4. Swing Support
5. Feedback.

Each of these 5 main categories is adjustable for the right and/or left sides of the body.

Joint Neutrals: Pressing the “Reset Neutrals” buttons will cause Indego to capture the current position of each joint and treat this stored angle as the joint’s neutral position (i.e. Indego will treat the stored position as though it were zero degrees of flexion or extension at each joint). This permits Indego to automatically calibrate itself to adjust for slight misalignment between the user and the Indego, or to adjust for users who walk with joint angles that differ from the anticipated.

[figure not shown]
Gravity Compensation: Reduces the weight of the user’s leg (i.e. making the user’s limb seem lighter during gait). The percentage of the user’s limb weight to be accounted for may be varied independently for each leg by adjusting the position of the Left Leg Support and Right Leg Support sliders. The amount of compensation is represented on a scale of 0 to 100 percent in 10 percent increments. Changing the support level adjusts the support for both upper- and lower leg compensation.

Stance Support: Stabilizes the stance limb by providing resistance to excessive knee flexion or hyperextension.

Swing Support: Provides an additional push at the hip or knee joints when gravity compensation is insufficient to achieve the desired joint excursion during swing. Flexion assistance becomes active as soon as the Indego detects that the user is attempting to take a step, and remains active until either the duration of the flexion assistance passes, or the user begins to extend the knee. Extension assistance is provided once the knee begins to extend, and lasts until the knee achieves adequate extension or until heel strike is detected.

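### The only analysis-population rule sets non-completers apart with no exception for safety data, so subjects who stop because of harm fall outside the main safety summary

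*Combined protocol and SAP*

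**What the plan says.** The Primary Objective in the Study Synopsis is a safety objective: "To demonstrate that the Indego® device is safe to use as a gait training intervention for persons with hemiplegia due to CVA". The results are intended for a 510(k) submission.

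The rule on who is analysed appears twice.

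- **Study Design.** When a subject does not complete all sessions, "an additional subject will be added to replace the person who did not complete the study". It then says: "Data for persons who did not complete all sessions for the study will be analyzed separately".
- **Statistical Measures.** "Forty subjects must complete all sessions for the study to be concluded". For a subject who cannot complete, "their data will be analyzed separately and reported as a sub set to the main report". The next sentence of that section names 40 participants as the basis for assessing the safety of the device.

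Three other statements bear on the point.

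- **Study Design** allows missed sessions to be rescheduled, within a limit: "The maximum amount of time the protocol may be interrupted or extended (due to illness, weather, other) is two weeks".
- **Safety Measures** says: "All Subject Adverse Events and Serious Adverse Events will be documented, reported and followed to resolution". A parallel item covers device-related events.
- **Statistical Measures** ends with a list of descriptive analyses that includes "gait characteristics and subject/device adverse events". It names no population.

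**The concern.** In a safety study, completion can depend on the outcome being measured. A subject who has an adverse event may stop because of it. A subject kept away for longer than the permitted interruption cannot complete within the protocol at all. Under the rule as written, both are replaced and moved to the subset, and the main report describes the 40 who got through every session.

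If subjects with an event stop more often than subjects without one, the event rate among completers is too low. For a submission that rests on safety, the main figure should not depend on who completed. Replacement makes this harder to see, because the main set always numbers 40, however many people used the device.

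**Working it through.** **The plan's own figure.** The only power figure is 0.87 for a matched-pairs t-test with n = 40, effect size 0.50 and alpha 0.05 (Statistical Measures). With 39 degrees of freedom and noncentrality 0.50 × √40 = 3.162, the noncentral t distribution gives 0.869 two-sided, so the figure reproduces. It covers the pre/post comparison only and says nothing about the safety population. It matters here only because the fix leaves it unchanged.

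**Reading the text.** Both statements of the rule refer to a non-completer's data in general. Neither separates safety from mobility data, and neither considers the reason for stopping. No section defines a safety set or an all-exposed set. The main set is therefore the 40 completers.

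**Illustration 1: what the main summary would show.** The documents give no withdrawal or event rate, so the inputs are assumed. Let k subjects stop because of harm and be replaced, and let 40 others complete without an event. The completer rate is 0/40 for every k, and the all-exposed rate is k/(40 + k). The intervals are exact (Clopper-Pearson) two-sided 95%. For 0/40 the upper limit is 1 − 0.025^(1/40) = 8.8%.

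| k | Completers | All exposed | 95% interval, all exposed |
|---|---|---|---|
| 1 | 0/40 | 1/41 = 2.4% | 0.1% to 12.9% |
| 2 | 0/40 | 2/42 = 4.8% | 0.6% to 16.2% |
| 4 | 0/40 | 4/44 = 9.1% | 2.5% to 21.7% |

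From k = 4 the all-exposed point estimate lies above the upper limit computed from completers alone.

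**Illustration 2: direction of the bias.** Let p be the true event risk, q the share of affected subjects who stop and r the share of unaffected subjects who stop. Then

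completer rate = p(1 − q) / [p(1 − q) + (1 − p)(1 − r)].

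With p = 0.10 assumed:

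| q | r | Calculation | Completer rate |
|---|---|---|---|
| 0.50 | 0 | 0.050/(0.050 + 0.900) | 5.3% |
| 0.50 | 0.10 | 0.050/(0.050 + 0.810) | 5.8% |
| 0.50 | 0.25 | 0.050/(0.050 + 0.675) | 6.9% |
| 0.25 | 0.25 | 0.075/(0.075 + 0.675) | 10.0% (no bias) |
| 0.10 | 0.25 | 0.090/(0.090 + 0.675) | 11.8% (reversed) |

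The completer rate is too low only when q exceeds r.

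**The case against.** The strongest reply is that the text has a second reading. Safety Measures requires every adverse event to be documented and reported, and the list of descriptive analyses includes adverse events without limiting them to completers. On that reading the completer rule governs only the pre/post tests, which need the final evaluation in session 6, and the defect is an unstated denominator. This does not carry. The Safety Measures item is a duty to document and follow up, and the descriptive list names no population. Neither overrides a rule written for all of a non-completer's data, in a section that goes on to tie device safety to 40 participants.

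Other parts of the reply stand as limits on the point.

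- Non-completers are reported as a subset, so a reader could add the two parts together. The data are separated from the main figure, not suppressed.
- Size and direction are unknown. Illustration 1 is an extreme case, with every event in a non-completer. The plan sets no numerical safety criterion that a different rate would cross.
- With six sessions, rescheduling and the permitted interruption, a subject with a brief event can still complete.
- Reasons for stopping are not among the items listed under Session Data, so tabulating them may need one added field. Nor is a safety contact described for a subject who stops attending, beyond following known events to resolution. A change of analysis set would not recover an event that first appears after that.

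**Conclusion.** The concern holds and must be fixed. As written, the plan makes the main safety summary depend on completion, and safety is the primary objective. This conclusion rests on the wording alone and needs no assumed rate.

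The numerical effect cannot be derived from the documents. Under the assumptions above, one to four harm-related stops would move the rate from 0% among completers to between 2.4% and 9.1% among all exposed subjects. An assumed 10% risk could appear as anything from 5.3% to 11.8%, depending on who stops. That uncertainty about direction is itself a reason to use a set that does not depend on completion.

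**What to change.** In Study Design and in Statistical Measures:

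1. State that the primary safety analysis in the main report includes every subject with at least one Indego exposure, whether or not the subject completed or was replaced. State whether the session 1 fit counts as exposure.
2. Report adverse events, falls and device malfunctions in that set, with its denominator.
3. Tabulate completion and reasons for stopping over all enrolled subjects.
4. Keep the 40 completers for the pre/post mobility tests, and label that a completer analysis.

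**Cost.** The change is wording in two sections, plus a field for the reason for stopping if none is collected. No extra subjects are needed. Adverse events, falls and device events are already recorded at each session, and the 40 completers and the 0.87 power are unaffected. The reported safety rate may turn out less favourable, so the change is most credible if made before results are known.

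### Fast gait speed and spasticity are re-measured only at session 6 and non-completers are replaced, so the main pre/post result describes completers only

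*Combined protocol and SAP*

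**What the plan says.** All references are to the combined protocol and SAP.

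- **Completion rule (Statistical Measures).** "Forty subjects must complete all sessions for the study to be concluded". For anyone who does not, "their data will be analyzed separately and reported as a sub set to the main report".
- **Replacement (Study Design).** If a subject does not finish, "an additional subject will be added to replace the person who did not complete the study". The same paragraph adds: "Data for persons who did not complete all sessions for the study will be analyzed separately".
- **Timing of the post-test (Study Design, session table).** The row for session 6 reads "Indego Training Session Final Evaluation". No other row contains a post-training evaluation, and none is tied to early stopping.
- **Spasticity (Session Data).** "Formal MAS only during sessions one and six"; the other sessions collect comments only.
- **Mobility (Measures and Session Data).** Two activity measures are named, FAC and fast gait speed from the 10 Meter Walk Test. The per-session list, introduced by "Within each of the six sessions, the following parameters will be also monitored and recorded", includes FAC but not gait speed.
- **Analysis (Statistical Measures).** Pre/post differences are tested by matched-pairs t-tests with 40 participants. No analysis of all treated subjects and no method for missing data is described.

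**The concern.** Membership of the main pre/post analysis is decided by something that happens after training begins. Poor response, pain or fatigue are plausible reasons to leave a gait-training programme. If they operate here, replacing leavers with finishers selects subjects who did better. The design is single-arm with subjects as their own control, so no comparison group would reveal this.

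The separate analysis of non-completers does not repair it, because the plan never collects a second gait speed or MAS from someone who stops before session 6. No later analysis can recover a measurement that was not taken.

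What is at stake is how the mobility and spasticity results can be read. They are listed as supportive and exploratory, but the primary endpoint also speaks of potential effectiveness, and the results are intended for a 510(k) submission covering persons after stroke. The point concerns these pre/post outcomes, not the safety summary.

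**Working it through.** **1. The plan's own figure.** Inputs from Statistical Measures: n = 40, effect size 0.50, alpha 0.05 (sidedness not stated), power 0.87. For a two-sided paired t-test, df = 39 and the noncentrality is 0.50 × √40 = 3.16. The noncentral t distribution gives power 0.869, which matches. The figure is sound and applies to 40 completers.

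**2. What exists for a subject who stops after session 3.** The contents of the final evaluation are not itemised, so the gait-speed row is inferred from the Measures list, the session table and the per-session list.

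| Measure | Baseline | Planned later value | Pre/post pair |
|---|---|---|---|
| Fast gait speed | session 1 | session 6 only | none |
| Formal MAS | session 1 | session 6 only | none |
| FAC | session 1 | every session | yes, to session 3 |

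**3. Size of a possible selection effect.** Let 40 completers have mean standardised change 0.50 (the plan's effect size, taken here as the completers' true change). Let k further subjects stop early with mean change m. Both k and m are assumptions.

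All-treated mean = (40 × 0.50 + k × m) / (40 + k)

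| k (total treated) | m = 0.50 | m = 0 | m = −0.50 |
|---|---|---|---|
| 5 (45) | 22.5/45 = 0.50 | 20/45 = 0.44 | 17.5/45 = 0.39 |
| 10 (50) | 25/50 = 0.50 | 20/50 = 0.40 | 15/50 = 0.30 |

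The completer analysis would show 0.50 in every cell. The overstatement equals the stopper fraction times (0.50 − m). It is zero when stoppers change as completers do.

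**4. Power of an all-treated analysis if every stopper were measured.** Let w = k/(40 + k), and take a within-group SD of 1. The variance of the change is 1 + w(1 − w)(0.50 − m)².

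- k = 5, m = 0: effect size 0.444/√1.0247 = 0.439, power 0.82.
- k = 10, m = 0: effect size 0.400/√1.04 = 0.392, power 0.78.
- m = 0.50: power 0.91 with 45 and 0.93 with 50.

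Replacement therefore preserves the stated power for completers, but it does not protect against selection.

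**The case against.** The strongest reply is that the analysis answers the question asked. The mobility hypothesis concerns change after six sessions, completers are the people it describes, and the completer rule and separate reporting are declared in advance. That stands, and it is why the completer analysis should be kept. It does not supply the missing measurements or show what happened among all who were treated.

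A second reply is that the outcomes are supportive and that an uncontrolled pre/post change, with concurrent therapies allowed and acute subjects enrolled, cannot be attributed to the device anyway. That limits the weight of the point without removing it.

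A reader might also infer more than the documents support:

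- **That nothing is measured after baseline until session 6.** FAC is recorded at every session.
- **That non-completers are hidden.** They are kept out of the main analysis but are reported as a subset.
- **That anyone who misses one session is lost despite having a session 6 evaluation.** Study Design calls for attempts to reschedule, allows up to two weeks of interruption or extension, and keeps the number of visits unchanged. Sessions are meant to be made up. This also limits attrition.
- **That stopping means intolerance.** Illness and weather are named as causes of interruption, and reasons for stopping are not otherwise addressed.

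**Conclusion.** The point holds for fast gait speed and formal MAS. The main result comes only from subjects who completed all six sessions, and the planned non-completer analysis has no pre/post value for either measure. This follows from the schedule and the completion rule without any assumption about dropout.

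Upward bias is plausible but not shown. The documents give no dropout rate, no breakdown of reasons and no outcomes for stoppers. Under the assumed cases, a completer change of 0.50 corresponds to 0.44 or 0.40 among all treated (5 or 10 stoppers with no change), to 0.39 or 0.30 if stoppers worsen by 0.50, and to 0.50 if they change as completers do. The stated power is not in error. This is an inexpensive improvement that has to be made before data are collected, not a flaw that invalidates the study.

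**What to change.** 1. For any subject who has had at least one Indego training session and stops early, do the existing final evaluation (fast gait speed, FAC, MAS, MMT) at the last attended session or once the decision to stop is known, if the subject is willing and able. Record the reason for stopping.
2. For each measure, report a pre/post analysis of all treated subjects who have a post-baseline value for that measure, beside the completer analysis. The completer analysis remains the one for the six-session hypothesis. Use per-session FAC for the FAC outcome only, since it cannot stand in for gait speed or MAS. Say whether the per-session FAC is taken before or after training, which the documents leave open.
3. State the numbers enrolled, replaced and missing next to each result.

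The cost is protocol wording and an evaluation already in the schedule, moved forward for those who stop. Some post-tests will follow fewer sessions, so the all-treated estimate may be slightly smaller. Some stoppers will decline and remain missing, so selection is reduced rather than removed. No rule on treatment or stopping changes.
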